Fruits and vegetables have also been studied for their antioxidant effects due to the phenolic and prebiotic compounds inherent to the foods. The phenolic and micronutrient compounds contribute to the effectiveness of fruits and vegetables as antioxidants. A 2013 study on the effect of increasing fruit and vegetable consumption found increased levels of -tocopherol, lutein, beta carotene, beta cryptoxanthin, and ascorbic acid through diet intervention. Increasing the amount of antioxidants in the diet can combat the effects of oxidative stress which contribute to the development of chronic disease. The beneficial compounds of fruits and vegetables remain obtainable in pressed fruit/vegetable juice. A 2017 study found pure pressed fruit and vegetable juices contained the necessary polyphenols and vitamins found in whole fruits and vegetables to maintain the positive relationship between fruit/vegetable consumption and lower incidence of chronic noncommunicable disease. Similar to studies with whole fruit, participants consuming pure fruit/vegetable juices had lower levels of lipid peroxidation and higher levels of most plasma/serum antioxidant vitamins. Therefore, pressed fruit/vegetable juices are an appropriate method through which to study the effects of fruit/vegetable consumption on the development of chronic disease.

Despite the popularity of 3-day juice fast, there is little existing literature delineating the effects of the diet intervention over other fasting protocols. 3-day juice fast programs qualify as a fast under the definition of fasting due to the low caloric intake of the participant. The 3-day juice fast program we will be utilizing provides approximately 800 -900 kcal per day, 60% and 70% less than the average recommended daily intake for women and men age 19-30, respectively. The purpose of this study is to delineate the mechanism through which juice fasting interventions affect change in methylation, gut microbiome, and inflammation markers.

STUDY ENDPOINTS:

The primary endpoints of the study are changes in epigenetic markers, gut microbiota, and biomarkers of inflammation and insulin resistance that may potentially occur after juice fasting. Secondary goals of the study include providing a foundation for future studies to examine the mechanisms of the intervention and test the intervention in a larger scale.

STUDY INTERVENTIONS / INVESTIGATIONAL AGENTS:

Group 1: Juice Fasting

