			Manganese: 22.80%
			5

PROCEDURES INVOLVED:

Up to 30 participants (15 males and 15 females) will be enrolled in the study and will be randomized into one of the three arms (we expect each arm will have three male and three female participants after attrition): the "juice fasting" arm, the "juice in addition to normal diet" arm, and the "caloric restriction diet" arm. Participants will come into the lab for an initial visit, during which they will complete questionnaires on their usual diet and demographics and will be informed about their assignment to one of the three arms.

In the "juice fasting" arm, participants will be given vegetable/fruit pressed juices and be instructed to engage in a three-day juice fast diet totaling 800-900 kcal-per-day (nutrient information of juices attached). The specific juices will be assigned for each day in order to maintain the calorie level. In the "juice in addition to normal diet" arm, participants will be given the same juice for three days but continue with their usual diet in addition to the juice. For this

arm, there is no restriction of caloric intake or restriction to liquid only. In the "caloric restriction diet" arm, participants will be on a whole-food plant-based diet totaling 800-900 kcal-per-day (matching the daily calories of juice fasting).

Packaged food and drink will be provided, delivered by the manufacturers (KitchFix and Pressed Vibrance), but participants will need to have access to their own food storage, such as a refrigerator. Deliveries will occur at a place and time of day specified by the participant to ensure delivery to the participant and immediate refrigeration, and both the participant and study coordinator will be notified when deliveries occur. Pressed Vibrance deliveries will be in cooler bags lined with ice packs on all sides, kept roughly 37-39 degrees Fahrenheit. KitchFix deliveries will be in cooler bags with a frozen water bottle, often delivered via refrigerated vehicle.

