In all three arms, the three-day diet intervention will be preceded and followed by three days of self-conducted elimination diet. The pre-intervention diet will encourage participants to eat a healthy, light diet for three days (basic instructions: eat only fresh raw or cooked fruits and vegetables (preferably organic), whole grains and eggs; drink 8 glasses of water a day; avoid or eliminate alcohol, caffeine, sugar, processed foods, dairy, red meat, and gluten). The post-intervention diet will instruct participants to gradually return to eating solid foods, and limit strenuous exercise (basic instructions: follow a diet similar to the pre-intervention elimination diet; day 1 after the intervention: eat fruits & green vegetables, and drink 8 glasses of water; day 2 add in: nuts, gluten-free grains like whole oats, quinoa, or brown rice; day 3 add in: organic meats, fish, & gluten-containing grains).

Biological samples and self-reported outcomes will be collected at four time points: baseline (prior to the first elimination diet period), pre-intervention (after the elimination diet and before the three-day intervention), post-intervention (after the intervention), and 14-day post-intervention. At each time point, participants will complete questionnaire on quality of life (PROMIS - Global Health Scale, which is an NIH measure on an individual's' overall physical and psychological well-being; see appendix) and collect their own saliva and stool samples. Participants will be given self-administered toolkits and be taught how to collect the samples at their first lab visit. At each of the four time points, the research assistant will coordinate the collection of cheek swabs and bloodspot samples. Stool samples will be collected using a premoistened wipe, with written instructions provided to participants, and both stool and saliva samples will be collected by the participant at home, then provided to the research assistant at their next visit.

Over the course of the study, participants will be instructed to keep a diet diary days one through nine to record their dietary intake of each day (diet diary forms with instructions attached), as well as fill out a modified version of the PROMIS Global Health Scale. During the intervention period, the research team will also contact the participants to check in with them. Participants will not need to record diet data for the fourteen day post intervention period.

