Weight, height and waist circumference measurements: These measurements will be done in a private setting by a trained research assistant.

Psychological questionnaires: Participants will be told that they can refuse to answer questions that they feel are too personal or that they feel would be too distressing to answer.

Adverse events: Participants will be asked to report significant adverse events as soon as possible to study staff, and will be provided with a study phone number for this purpose. Study physicians will be available to study staff by pager if needed to assess possible adverse events and provide clinical input, including calling participants if indicated.

POTENTIAL BENEFITS TO PARTICIPANTS:

Participants may or may not experience health benefits from juice cleansing and/or fasting. Participants will receive juice or packaged caloric-restriction meals for the 3-day intervention. They will also be compensated for their participation in the study (up to \$100). Other possible immediate and/or direct benefits to participants and society at large include: health and lifestyle changes may occur as a result of participation; knowledge may be gained about their health and health conditions; feeling of contribution to knowledge in the health or social sciences field.

DATA AND SPECIMEN MANAGEMENT AND CONFIDENTIALITY:

Biological sample collection/storage and shipment: All biological samples that will be used for this project will be collected and then de-identified and labeled with the following information: patient ID, date of collection, time of collection, and time point (baseline, pre, post and 3 days post). All samples will be stored in a -80C freezer in the lab located at Northwestern University, Department of Medical Social Sciences, [name] until ready for transfer for laboratory analysis.

Data handling for Methylation/Microbiome Testing

One set of de-identified DNA samples of stool, bloodspot, cheek swab, and saliva will be collected in sealed plastic bags and placed with a freeze pack inside of an insulated shipping container. The container will be shipped to Northwestern University NUseq Core Facility, [name] for laboratory assays.

Data handling for Glycemic and Inflammatory Biomarker Testing

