One set of de-identified labeled bloodspot samples will be collected in sealed plastic bags and placed with a freeze pack inside of an insulated shipping container. We will seal the box tightly with tape and ship specimens via courier to:

Laboratory for Human Biology Research at Northwestern University Department of Anthropology, [name]; [contact]

Contact: [name]; email: [contact]

No names or individual identities will be used in publications resulting from the study. Physical records will be kept in an area accessible only to research staff. Research data will be stored on a secure, HIPAA-compliant server and drive with monitored and controlled access for study staff and investigators. Survey data will be hosted on secure servers. A key linking study ID to participant names will be kept in a password-protected file on a secure FSM server, separate from study data.

Biomarker Testing

Whole Blood Testing

Inflammatory Stress and Glycemic Biomarkers will include (C-reactive protein, interleukin-6, insulin, leptin). These biomarkers will be assayed using the finger prick/filter paper collection procedure. Blood spot samples will be collected at each scheduled time point in the protocol at the Osher Center for Integrative Medicine clinic or a mutually determined region on the Northwestern campus (in order to accommodate participants' schedules). Throughout all stages of blood collection and processing, Universal Precautions will be followed. Each participant's finger will be cleaned with alcohol and then pricked with a sterile, disposable, widely available micro-lancet commonly used by diabetics. Five drops of whole blood will be collected on standardized filter paper.

Samples will be dried overnight and stored in a -80C freezer at the Northwestern University, Department of Medical Social Sciences, [name] until analysis, at which time specified samples will be transported to the appropriate lab.

Blood spot samples will be analyzed using previously validated ELISA protocols previously developed for use with dried blood spots. Samples will be analyzed for inflammatory and glycemic index markers using a high sensitivity immunoturbidimetric assay on the Hitachi 917 analyzer (Roche Diagnostics—Indianapolis, IN) and the Luminex® 200™ System (Luminex Corporation, Austin, TX), separately. All samples are run in duplicates.

Physiologic Measures

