We will measure systolic and diastolic blood pressure, which will be measured manually using a stethoscope and blood pressure cuff. Participants will be assisted in sliding their left arm through the cuff, positioning it 0.5-inches above the elbow, and securing it with Velcro material. They will place their arm on a table so that the cuff is positioned at the same level as their heart. Pulse will Version #:1.4 Version Date: 05/22/2018

also be checked manually by placing the tips of the index and second fingers of one hand on the inside wrist of the patient and positioning the fingers just below the base of the thumb to take the radial pulse at the patient's wrist.

Weight and waist circumference will be measured at each timepoint. Waist circumference will be measured according to CDC guidelines: the participant will stand, and a tape measure will be placed horizontally around their middle, just above the hip bones. It will be kept snug, but not compressing the skin, and measurement will be taken just after the participant exhales. Height will be measured at the initial intake.

DNA methylation (blood)

We will use QIAamp DNA Blood Midi Kit (Qiagen) to extract cfDNA from blood samples of study participants according to the manufacturer's protocol. We will then undertake unbiased, genome-wide interrogation of DNA methylation using Illumina's newly released Infinium Methylation EPIC BeadChip (EPIC array), an updated version of the widely used Illumina 450K array (terminated in March 2016). The EPIC array covers over 850K methylation sites across the human genome and includes CpG sites outside of CpG islands, non-CpG methylated sites identified in human stem cells, sites differentially methylated in tumor cells, FANTOM5 (Functional Annotation of Mammalian Genome) enhancers, ENCODE (Encyclopedia of DNA Elements) open chromatin and enhancers, DNase hypersensitive sites, microRNA promoter regions, as well as 93% of the content contained in the old Illumina 450K array.

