The Illumina Genome Studio-generated detection p-values will be used to distinguish reliable and unreliable probe signals, and to identify failed samples. We will remove samples that contain >5% failed probes at detection p>0.01, as well as CpG sites that failed in >5% of samples (i.e., calling rate <95%). CpG probes mapped to ambiguous locations in the human genome will be detected and removed. To avoid potential SNP-in-probes bias, we will also exclude CpG probes containing common SNPs (MAF [minor allele frequency] >0.01) based on dbSNP. The final analysis set will include only CpG probes located on autosomes. The level of methylation, represented by the ratio of methylated signal to total signal and the M-value (log2 ratio of methylated signal over unmethylated signal) will be determined for each interrogated locus. We will also conduct analyses using the β-value (i.e., the proportion of modified signal in total signals from 0 to 1), which has a more straightforward biological interpretation. The methylation levels will be quantile-normalized across all samples. Potential batch effects and blood cell subpopulation proportion estimated by Houseman's method 41 will be corrected using ComBat.42 To account for multiple comparison issue, we may 1) narrow down the genome- wide scan (~300,000 unambiguous autosomal CpGs) to those well-annotated genic CpG sites (~100,000); and 2) further narrow down to highly variable CpG sites, for example top 10% of highly variable (informative) CpGs (~10,000 CpGs) across the samples.

DNA extraction, 16S rRNA sequencing and microbiome analysis

Saliva samples and buccal cell DNA will be extracted using QIAamp DNA Mini Kit (Qiagen). Stool sample DNA will be extracted using QIAamp DNA Stool Mini Kit (Qiagen). The quality and quantity of the DNA will be examined using Nanodrop spectrophotometer (ThermoFisher Scientific). 16S rRNA amplicon library will be prepared using Nextera XT DNA Library Preparation Kit (Illumina) following the manufactures protocol. DNA (100 ng) will be used as template for PCR

to amplify the 16S rRNA region. The 16S rRNA amplicon libraries will then be sequenced on a MiSeq system (Illumine). For the 16S rRNA amplicon analysis, the individual library read files will be paired and combined in silico (16S–total) and analyzed for taxonomic annotation using the RDP tool.

PROVISIONS TO MONITOR THE DATA TO ENSURE THE SAFETY OF PARTICIPANTS:

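### The protocol assigns the correction of estimated blood cell proportions to ComBat, a batch method that, read literally, does not remove them

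*Protocol*

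**What the plan says.** The protocol makes blood methylation part of its primary outcome (STUDY ENDPOINTS): "The primary endpoints of the study are changes in epigenetic markers", alongside microbiota and the inflammatory and insulin-resistance markers. Blood is taken at four time points, and the expected yield is six completers per arm (PROCEDURES INVOLVED): "we expect each arm will have three male and three female participants after attrition".

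DNA methylation (blood) lists the preprocessing steps: probe and sample quality control, quantile normalisation, and then "Potential batch effects and blood cell subpopulation proportion estimated by Houseman's method 41 will be corrected using ComBat". No regression adjustment, residualisation or other operation on the estimated cell proportions is named there or elsewhere in the protocol. The quantile normalisation does not use them.

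The next sentence offers options for easing multiplicity, one of which is to "further narrow down to highly variable CpG sites, for example top 10% of highly variable (informative) CpGs", leaving about 10,000 sites.

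**The concern.** The sentence gives one tool two tasks, and the tool does only the first. ComBat estimates location and scale differences between the levels of a categorical batch and removes them. Houseman estimates are continuous proportions that vary from sample to sample within a batch. An analyst who follows the sentence would produce data described as corrected for cell mix that still carry most of it.

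Bulk-blood methylation is an average over cell types. If a diet changes the mix of white cells, bulk methylation changes at every site where the cell types differ, even if no cell changes its methylation. A result believed to be cell-mix-corrected would then be read as change within cells. The variability filter raises a second, smaller matter: if cell mix is left in, ranking by variance favours sites that track it.

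**Working it through.** The protocol gives no figure on this point, so there is none to reproduce. The check is how ComBat treats the proportions, followed by its size under assumed inputs.

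**1. What ComBat does.** For site *g*, batch *i* and sample *j*, the model is Y = α_g + Xβ_g + γ_gi + δ_gi·ε. The adjusted value is the standardised residual with the batch terms γ and δ removed, after which α_g + Xβ_g is added back.
- Proportions placed in X are added back, so they are kept by design.
- Proportions not in X sit in ε. They are touched only so far as batches happen to differ in mean proportion, or are rescaled with δ.

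**2. Share of the cell-mix slope left, proportions not in X.** From the protocol: 18 completers × 4 time points = 72 samples. Assumed: *k* batches with samples allocated at random. Centring each batch leaves on average 1 − (k − 1)/(n − 1) of the slope:

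| Batches | Centring only, by formula | Simulated, mean-only | Simulated, parametric empirical Bayes | Simulated, no shrinkage |
|---|---|---|---|---|
| 2 | 1 − 1/71 = 0.986 | 0.983 | 0.969 | 0.964 |
| 3 | 1 − 2/71 = 0.972 | 0.977 | 0.938 | 0.949 |
| 6 | 1 − 5/71 = 0.930 | 0.934 | 0.879 | 0.885 |
| 9 | 1 − 8/71 = 0.887 | 0.895 | 0.817 | 0.802 |

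The simulations assume proportion SD 0.06, batch SD 0.02, noise SD 0.015 and cell-type differences uniform on ±0.6 beta. The range is 80-98%. If each batch holds whole participants, it is 63-96%.

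**3. Proportions in X.** The slope retained was 0.999-1.002, so nothing is removed.

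**4. What does remove it.** A separate simulation used 72 samples treated as independent, 9 batches and an assumed 0.04 shift in one cell fraction (SD 0.07). The median R² between methylation and cell fraction was 0.27 uncorrected, 0.35 after ComBat on batch only, 0.47 after ComBat with the fraction as covariate, and 0.00 after regressing the fraction out. Clearing batch noise makes the cell signal more visible, not less.

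**5. Size of a misreading.** Error in a within-cell reading = D × Δ × r. D is the cell-type difference at the site (assumed 0.3 beta), Δ the between-arm difference in cell-mix shift, and r the share left in a between-arm difference in change. Without covariates, the simulated r was about 0.70-0.99 for random layouts and 0.90-1.00 for whole participants per batch.

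| Δ (points) | r = 1 | r = 0.70 |
|---|---|---|
| 0 | 0 | 0 |
| 3 | 0.3 × 0.03 = 0.009 | 0.006 |
| 5 | 0.3 × 0.05 = 0.015 | 0.011 |
| 10 | 0.3 × 0.10 = 0.030 | 0.021 |

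**6. Variability filter.** Assume 20,000 sites and 72 samples, with 5%, 10% or 20% of sites differing by cell type. Those sites then fill 22%, 44% or 67% of the top tenth if cell mix is left in, against 5%, 10% or 21% once it is regressed out. No difference between arms is needed.

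**The case against.** The best defence is that the sentence compresses two steps: Houseman's method to estimate the proportions and ComBat for batch, with the proportions meant for a later model. The protocol states no per-CpG model, so there is no place where covariates could appear. Such a model, the number of proportions and the order of ranking are ordinary content of a statistical analysis plan, and one may exist. This stands as far as it goes, and nothing here is held against the protocol for leaving the model out. But the protocol does not leave the cell-mix correction open. It commits to one and names a method that does not deliver it. That wording is open to objection whatever a later plan says.

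The documents do not support several stronger readings:
- **That the methylation endpoint is biased.** The endpoint is change in epigenetic markers, not change within cells. The randomised bulk-blood difference is an unbiased total effect whether or not cell mix moves. Rejection rates above nominal in a simulation with a cell-mix shift are false only against a within-cell null.
- **That many false sites would be declared.** A count needs the shift, the cell-type difference and the share of sites that differ by cell type. The protocol gives none of these.
- **That adjusting costs power only when the shift is large.** Assume 6 v 6, a 0.03 beta effect, noise SD 0.015 and proportion-change SD 0.04. At 5e-6 (0.05/10,000), adjusted rejection is below unadjusted at 3, 5 and 10 points: 0.0028 v 0.0037, 0.0018 v 0.0062 and 0.0005 v 0.0289. The unadjusted figures also include rejections caused by the shift itself, so this is not a clean comparison of power.
- **That the filter is an error.** It is optional, and variable sites that track cell mix are legitimate for a bulk-blood endpoint.

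**Conclusion.** The concern holds as a wrong statement of method, and it is minor. Followed literally, the plan does not deliver the cell-mix correction that it promises. That direction follows from how ComBat works and does not depend on assumptions. The sizes do: 80-98% of the slope left in for randomly allocated batches, and 0 to about 0.03 beta of error in a within-cell reading for shifts of 0 to 10 points at an assumed 0.3 beta cell-type difference. With no differential shift that misreading does not arise, and the protocol gives no figure for a shift. Only the blood methylation part of the primary endpoints is touched.

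Two editorial matters in the same section are separate and add no weight. First, the extract is described as cell-free DNA ("to extract cfDNA from blood samples of study participants"), while the blood is collected as dried whole-blood spots: "Five drops of whole blood will be collected on standardized filter paper" (Whole Blood Testing), "One set of de-identified DNA samples of stool, bloodspot, cheek swab, and saliva will be collected in sealed plastic bags" (Data handling for Methylation/Microbiome Testing) and "the research assistant will coordinate the collection of cheek swabs and bloodspot samples" (PROCEDURES INVOLVED). Cell deconvolution also presumes DNA from blood cells. Second, citations 41 and 42 have no entry in a reference list that ends at 5.

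**What to change.** Replace the sentence with two. ComBat is applied for array or plate batch only. A small, prespecified number of estimated cell proportions (or their changes, if change is modelled) enter the per-CpG model as covariates. Report results with and without them, labelled as the cell-mix-adjusted and the total bulk-blood effect. If the variability filter is used, rank sites after batch and cell mix have been removed. Separately, state which DNA is extracted, reconcile the sections named above, and correct the two citations.

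The drafting cost is a few sentences. The statistical costs are two:
- **Degrees of freedom.** With 18 completers and three arm means, 18 − 3 = 15 residual degrees of freedom remain. One proportion leaves 14 and five leave 10, which is why the number should be small and fixed in advance.
- **Estimand.** Proportions measured after the diet starts are post-randomisation variables. The adjusted result therefore answers a different question from the randomised comparison, and should accompany the total effect, not replace it.
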